2.3. Rationale for Combining Radiation Therapy with Immune therapy

While these findings are encouraging, the fact that only a minority of patients will respond to checkpoint inhibitors alone highlights that other barriers to immune stimulation exist. Radiation therapy has been combined with immune therapy to overcome some of these barriers in both preclinical and clinical studies.¹²⁻¹⁴ Radiation may help to break up the dense stromal barrier and acidic microenvironment surrounding tumors that is hostile to T-cell function, thus better mobilizing antigens and immune effector cells and activating the immune system. These benefits are not only restricted to the local area of irradiation, but also have an abscopal/systemic effect on cancer outside of the irradiated area.¹³⁻¹⁷ Radiation is in many ways uniquely suited to combine with immune therapy, since surgery removes the tumor and thus the antigenic source, and many chemotherapeutic agents are toxic to the host immune system. Radiation can upregulate targets of the immune system, augment their antigen presentation, and cause immune cell infiltration into the tumor.¹⁵⁻¹⁷ Altogether, these radiation-induced changes could lead to activation and proliferation of cytotoxic T-cells in an antigen-specific fashion in draining lymph nodes.¹⁸⁻²¹ The evolution of radiation therapy from serving as a purely locoregional therapy to a modality that can also stimulate a systemic cancer response represents an important innovation in oncology. However, the optimal way to combine immune checkpoint inhibitors and radiation therapy is poorly understood, and there is little prospective data evaluating its efficacy in patients, which is the rationale for performing this study. We hypothesize that this combination therapy will result in higher response rates, longer duration of response, and lengthened overall survival compared with previous studies utilizing immune checkpoint inhibitors alone.

2.4. Approach to Radiation Therapy Delivery

In standard clinical practice, the goal of radiotherapy in a patient with metastatic lung cancer is predominantly palliative for relief of symptoms. Quality of life is as important as longevity of life, and as such the radiation therapy administered in this trial will take into account quality of life, symptom relief, and minimizing morbidity along with the primary study goal of inducing an enhanced systemic immune response. We believe that these objectives will be best achieved by giving the treating physician discretion over the treated tumor site and choice of dose-fractionation used, within a set of guidelines.

Preclinical data suggest that a shorter course of hypofractionated radiation therapy in 5

fractions or fewer is more immune-stimulatory, whereas a longer course of conventionally fractionated radiation is more immunosuppressive, through their differential effects on the up- and down-regulation of CD8 T-cells, Treg and MDSC cells, and expression of OX40, PD-L1, and MHC-1.²²⁻²⁴ Fractionated courses are also superior to a single fraction treatment in stimulating an abscopal effect.²² As such, for the purposes of this study, we will use a dose of 6-12Gy per fraction in 3 fractions (total dose 18-36 Gy) or 4-10 Gy per fraction in 5 fractions (total dose 20-50 Gy) to be completed over the course of 3-21 days. This variety of regimens offers a biologically effective dose (BED) range of 28-100 for early responding tissue (which correlates with tumor control) and 47-217 for late responding tissue (which correlates with side effects). This will give the treating physician a full range of options, such that an adequate dose can be given to the tumor while meeting all dose constraints of normal organs. The optimal hypofractionated radiation regimen is unknown, and there is some evidence that lower dose (and thus less ablative) regimens that would result in inferior local control may actually be more systemically immune-stimulating.²⁴ As such, regimens with a lower BED will be favored for this study, with the exception of situations in which improved local control to palliate symptoms is also a priority. Higher BED regimens may also be considered for larger size tumors and more rapidly growing tumors. This general preference for lower dose regimens will also have the favorable consequence of reducing the morbidity of therapy. Visceral metastases or metastases in organs involved in the immune system (e.g. liver) will be targeted preferentially over bone metastases due to the increased likelihood of an abscopal effect that has been previously reported for tumors in these sites.^{13-14, 25} If a bone metastasis requires treatment for palliative purposes we advise also treating a visceral metastasis concurrently. Brain metastases will be treated according to standard of care if they develop during the period of trial enrollment, but because there is little evidence to suggest that treating a brain metastasis can elicit an extracranial systemic response, we advise also treating a visceral metastasis concurrently to increase the likelihood of an abscopal effect.

Finally, subsequent courses of radiation will also be delivered as part of this study in patients who are not having a systemic response to immune therapy or who are experiencing progressive disease. The rationale for these subsequent courses of radiation is to provide a frequent source of antigenic stimulation to potentially elicit an enhanced immune response. There is evidence to suggest that treatment of multiple lesions with SBRT in the metastatic setting has a survival benefit in lung cancer,²⁶ and scheduled radiation therapy has improved survival in other malignancies as well.²⁷

2.5. Background and rationale of correlative studies

In consenting patients, peripheral blood samples will also be collected at the time of any change in response status as assessed on follow-up imaging studies in order to correlate the biological effects of treatment to response, and potentially help characterize optimal treatment delivery. Preclinical data suggests that immune checkpoint inhibitors increase the quantity of the activated cytotoxic T-cell subpopulation, with a higher CD8/Treg ratio correlating with more robust immune activation.²⁸⁻²⁹ Additionally, M1/TH1 pro-inflammatory iNOS+ macrophages may also be recruited to a tumor and involved in cell-killing in this clinical context.³⁰⁻³¹ As such, we will use flow cytometry to characterize

levels of circulating CD4+, CD8+ and Treg T-cell subsets, as well as iNOS+/CD80+ macrophages. Changes in cytokine and chemokine levels specific for immune cell trafficking have not been well studied in patients receiving immune checkpoint inhibitors or radiation, so we will also evaluate for levels of circulating cytokines (HGF, TGF- β 1, TGF- β 2, TGF- β 3) and chemokines (CCL2 for M1 macrophages, and CXCL9, CXCL10, and CXCL11 for T-cells). Finally, the clonality and diversity of the T-cell receptor (TCR) CDR3 region may help determine the specific lung cancer antigens and host immune response that was triggered by immune therapy and radiation. We will use next generation sequencing of the circulating T-cells immune-repertoire (i-repertoire) to better understand the evolution of tumor response during the course of treatment.

3. STUDY DESIGN

3.1. Study Design

This will be a Phase II prospective non-randomized clinical trial, with the primary objective being to assess the efficacy of combined checkpoint inhibitor immune therapy and hypofractionated radiation therapy in patients with Stage IV NSCLC. Toxicity is a secondary endpoint since the doses of radiotherapy to be used are within the realm of standard of care, and available medical literature suggests that the combination of radiation therapy with various immunomodulatory agents does not lead to excessive safety issues that would warrant a Phase I study.^{14, 20, 23, 32-37} Since there is limited prospective clinical data on this approach in patients we felt that a randomized Phase III approach is not justifiable at present. Patients may be enrolled into this study before initiation of immune therapy (with radiation administered to one target lesion, starting at any time between the first and second cycles of immune therapy).

3.2. Number of Subjects

Approximately 33 subjects will be enrolled in this trial.

3.3. Expected Duration of Treatment and Subject Participation

Each course of radiation therapy will be 3-5 fractions delivered over 3-21 days. The first course of radiation will be initiated at any time point between the date of cycle 1 of immune therapy through the date of cycle 2 of immune therapy. The duration of immune therapy administration and the number of courses of radiation therapy that a subject receives will be dependent upon the subject's response to prior treatment. There is no specific maximum number of cycles of immune therapy if a patient continues to respond to treatment, or courses of radiation therapy if a patient has persistent stable disease on imaging. Progressive disease will be defined per irRC criteria as assessed by two imaging studies \geq 4 weeks apart. Because abscopal responses have been reported even when the radiation is given after the immune therapy was completed, a final course of radiation therapy will be offered to patients at the time of progressive disease on imaging.³⁸⁻³⁹ Subsequent therapy decisions will be at the discretion of the treating physicians, including the option of continuing the immune therapy past progression if clinically indicated.

The radiation therapy or immune therapy may be cancelled or discontinued at any point if no longer medically advisable due to intercurrent illness, toxicity/adverse event, decline in performance status, pregnancy, the best interests of the patient, or death. Subjects may also withdraw consent from treatment (partial consent) or from the study (full consent).

3.4. Duration of Follow-Up

Follow-up of subjects should continue for 30 days after systemic disease progression or initiation of an alternate systemic therapy (whichever comes first). After the study period, the sponsor-investigator may still obtain data from a subject's medical records or by phone call in order to document overall survival per patient agreement. Any adverse events experienced after a patient has discontinued the study treatment will be followed until resolution, stabilization, or until it has been determined that the study treatment or participation is not the cause. Serious adverse events that are still ongoing at the end of the study period will necessitate follow-up to determine the final outcome. Any serious adverse event that occurs after the study period and is considered to be possibly related to the study treatment or study participation will be recorded and reported immediately.

3.5. Overall Duration of the Study

The study begins when the first subject signs the ICF. The primary analysis will occur when all subjects have completed the surveillance period and the last subject experiences progressive disease. Complete enrollment is expected over a 2 year period.

3.6. Study Termination

The investigator and sponsor retain the right to temporarily suspend or terminate study participation at any time. The date and reason for discontinuation must be documented. The investigator is to notify the institutional review board (IRB)/independent ethics committee (IEC) in writing of the study's completion or early termination, send a copy of the notification to the sponsor or sponsor's designee, and retain 1 copy for the site study regulatory file. Every effort should be made to complete the appropriate assessments.

4.1. Inclusion Criteria

Subjects must meet all of the following inclusion criteria to be eligible for enrollment:

- ____ 4.1.1 Subjects must have Stage IV (metastatic) histology- or cytology-confirmed NSCLC. The tumor type must be confirmed by biopsy but the stage may be based on biopsy or imaging.
- ____ 4.1.2 Subjects must have measurable disease of at least 1.0 cm in greatest dimension in at least 2 previously non-irradiated sites (except for lymph nodes, in which the short-axis dimension must be at least 1.5cm).
- ____ 4.1.3 Subjects must be planned to receive standard of care checkpoint inhibitor immune therapy.
- ____ 4.1.4 Subjects must be age \geq 18 years since lung cancer is uncommon in children and likely to have different biologic properties and response to therapy in this age group.
- ____ 4.1.5 Subjects must have ECOG Performance status 0-2 [See [Appendix A](#)].
- ____ 4.1.6 Subjects must have life expectancy greater than 3 months
- ____ 4.1.7 Subjects must have adequate organ and marrow function as defined below within one month of study entry:
 - Hemoglobin \geq 8.0 g/dL
 - Leukocytes \geq 2,000/mcL
 - Absolute neutrophil count \geq 1,000/mcL
 - Platelet count \geq 50,000/mcL
 - Total bilirubin \leq 3.0 X institutional upper limit of normal, with the exception that patients with Gilbert disease may have a serum bilirubin \leq 6 X upper limit of normal
 - AST (SGOT) and ALT (SGPT) \leq 3 X institutional upper limit of normal (or \leq 5 X institutional upper limit of normal if liver metastases are present)
 - Serum Creatinine \leq 3.0 X institutional upper limit of normal
- ____ 4.1.9 Subjects must have the ability to understand and the willingness to sign a written informed consent document.

4.2 Exclusion Criteria

The presence of any of the following will exclude a subject from study enrollment.

- ____ 4.2.1 Subjects with active autoimmune disease (e.g. inflammatory bowel disease, rheumatoid arthritis, scleroderma, systemic lupus erythematosus, or autoimmune vasculitis), primary immunodeficiency syndrome, HIV/AIDS, or hepatitis B or C. Acknowledgement of any of these conditions is sufficient to exclude the patient from the study and no specific testing to exclude these conditions is required unless the patient expresses uncertainty about their presence.
- ____ 4.2.2 Subjects with oral corticosteroid dependency. Use of immunosuppressive doses of systemic medications within 7 days prior to starting study drug. Subjects are permitted to enroll if lower doses of systemic corticosteroids (< 10 mg/day

- prednisone equivalents) are used within 7 days prior to study drug administration. Inhaled or topical steroids and adrenal replacement doses > 10 mg daily prednisone equivalents are permitted in the absence of active autoimmune disease. Short-term steroids used to enable the use of IV contrast for an imaging study are permitted.
- 4.2.3 Prior treatment with any antibody or drug targeting T-cell costimulation or immune checkpoint pathways (anti-PD-1, anti-PD-L1, anti-PD-L2, anti-CTLA-4, etc), or subjects actively receiving any other investigational cancer-directed agent, Interleukin-2, or immunosuppressive agents.
- 4.2.4 Subjects with uncontrolled or untreated active brain metastases/CNS disease will be excluded from this clinical trial because of their poor prognosis and because they often develop progressive neurologic dysfunction that would confound the evaluation of neurologic and other adverse events. Patients with previously treated brain metastases (by whole brain radiation and/or stereotactic radiosurgery) are eligible if the treatment was greater than 7 days from enrollment. In this case, imaging to confirm intracranial response to therapy is not required as long as the patient does not have any worsening neurologic symptoms. Of note, if brain metastases develop while the patient is enrolled on this study and they are treated, the patient may continue participation in this study at the discretion of the treating physicians.
- 4.2.5 Subjects with uncontrolled intercurrent illness including, but not limited to, ongoing or active infection, symptomatic congestive heart failure, unstable angina pectoris, cardiac arrhythmia, or psychiatric illness/social situations that would limit compliance with study requirements.
- 4.2.6 Subjects who are pregnant are excluded from this study because radiation therapy has the potential for teratogenic or abortifacient effects. Women of childbearing potential must be using an adequate method of contraception to avoid pregnancy throughout the study and for up to 8 weeks after the last treatment.

4.3 Inclusion of Women and Minorities

Both men and women of all races and ethnic groups are eligible for this trial. It is the policy of the Mary Babb Randolph Cancer Center to strive for gender and minority patient participation that represents the population of West Virginia in all clinical investigations. Between January 2015 and December 2015, 233 patients were enrolled onto clinical trials at the Mary Babb Randolph Cancer Center. Of these patients 55% percent were female and 3% percent were members of minority ethnic groups. It is anticipated that a similar or greater proportion of patients on this study will be female and/or members of ethnic minorities. It is important to recognize that according to the 2014 US Census Bureau (available at <http://quickfacts.census.gov>) that the State of West Virginia minority ethnic group (e.g., not limited to African American and Hispanic) population is 3.6% Black (national average 13.2%) and 1.5% Hispanic (national average 17.4%). The majority of Black West Virginians live in the central and southern part of the state and Gilmer County is the only county in WV whose Black population approaches the national average.

4.4 Registration

At the point of registration, the study coordinator will complete registration in the OnCore database, including demographic, consent and on-study information.

The patient will be assigned a unique sequence number for the study prior to the initiation of the study treatment.

For those subjects who are consented, but not enrolled, the reason for exclusion must be recorded.

All source documents that support eligibility, signed informed consent/HIPAA and signed eligibility checklist must be available for review and verification by the quality coordinator prior to starting therapy.

Patient Travel Reimbursement

Travel reimbursement may be offered to patients on trial. Due to the limited travel funds available, travel reimbursement will be reviewed on case by case basis by the Principal Investigator.

5. TREATMENT PLAN

5.1. Initial Radiation Therapy

5.1.1 Dose-fractionation: The initial course of radiation therapy will be administered in 3 or 5 fractions over 3-21 days, at a recommended dose of 6-12 Gy per fraction for 3 total fractions (total dose 18-36 Gy) or 4-10 Gy per fraction for 5 total fractions (total dose 20-50 Gy). Dose-fractionation schemes with a lower BED will be favored, with the exception of situations in which improved local control to palliate symptoms is also a priority for a given patient. Higher BED regimens may also be considered for larger size tumors and more rapidly growing tumors.

5.1.2 Targeted Site: Visceral metastases or metastases in organs involved in the immune system (e.g. liver, lymph nodes) will be targeted preferentially. If a bone or brain metastasis develops while the patient is enrolled in this trial and requires treatment for palliative purposes, we advise also treating a visceral metastasis.

5.1.3 Radiotherapy Technique: Stereotactic body radiation therapy (SBRT) will be the favored treatment delivery technique due to its high conformality to a target volume and avoidance of organs-at-risk (OAR) of toxicity. Other techniques, like 3-dimensional conformal radiotherapy (3DCRT) and intensity modulated radiation therapy (IMRT), will be permitted with the caveat that the patient will, irrespective of technique, undergo CT simulation for treatment planning using SBRT immobilization devices, undergo daily image guidance to confirm the positioning of the tumor prior to treatment, and the plans must meet standard 3 or 5 fraction SBRT dose constraints to normal tissues. The use of 4D-CT and respiratory motion management for treatment planning and delivery are encouraged as necessary.

5.1.4 Treatment Planning: All patients will undergo CT simulation using SBRT immobilization devices. Target volumes (i.e. GTV, CTV, ITV, PTV) will be delineated at the discretion of the treating physician. In general, minimal or no margin should be added

for microscopic disease extension in this setting, with the focus on covering gross disease plus an appropriate margin to encompass tumor motion and any physical setup uncertainties. OARs should be contoured according to standard guidelines provided by NRG Oncology for clinical trials.⁴⁰ Megavoltage photons of at least 6MV will be used for all treatment plans. Ideally 95% of the planning target volume (PTV) should receive 100% of the prescribed dose, and all OAR constraints detailed in [Appendix B](#) must be achieved in order to minimize the risk of toxicity. In patients receiving multiple courses of radiation therapy, there will be an assumption of no tissue recovery, and the total dose to any organ from the sum of all radiotherapy courses will need to achieve the dose limits for a single course of hypofractionated radiation therapy as described in [Appendix B](#).

5.1.5 Treatment Delivery: The thoracic radiation oncologist or his/her designated physician is required to be present at the console to review the daily CT and projection images prior to each treatment. A brief documentation of the patient set up is required in the treatment monitoring system of each institution by the treating physician.

5.1.6 Coordination of Radiation with Immune Therapy: The first course of radiation will be initiated at any time point between the date of cycle 1 of immune therapy through the date of cycle 2 of immune therapy.

5.2. Standard of Care Immune Checkpoint Inhibitors

Immune checkpoint inhibitors that are FDA approved for use in patients with metastatic NSCLC will be acceptable for use concurrently with radiotherapy in this trial. The choice of agents will be at the treating medical oncologist's discretion, and include:

- Nivolumab 240 mg once every 2 weeks (14 day cycle) or 480 mg once every 4 weeks (28 day cycle)
- Pembrolizumab 200 mg once every 3 weeks (21 day cycle)
- Atezolizumab 1200 mg once every 3 weeks (21 day cycle)

These agents should be continued per standard of care until either disease progression or unacceptable toxicity. In the case of Pembrolizumab, it is also recommended that patients should be on the drug for no more than 24 months even if there is no evidence of disease progression. Pembrolizumab may also be used in combination with Pemetrexed and Carboplatin for the first-line treatment of metastatic non-squamous NSCLC. If any of the immune therapy agents are permanently discontinued at any point, a final course of radiation therapy should be offered to the patient before switching to an alternative therapy. While the patient is receiving immune therapy, no other investigational or commercial agents or therapies may be administered with the intent to treat the subject's malignancy.

5.3. Subsequent Response-Adapted Radiation Therapy

Any patient who completes the initial course of radiation therapy and continues on one of the immune checkpoint inhibitors described above will be eligible for subsequent course(s) of radiation therapy to a different lesion that was not previously irradiated based on the results of follow-up imaging studies detailed below and in section 11.

- Patients with a partial or complete response per irRC criteria will be observed without any further radiation therapy until progression.
- Patients with stable disease per irRC criteria will undergo an additional course of radiation therapy given concurrently with the next cycle of immune checkpoint

- therapy, and then continue the immune therapy as above. Each subsequent course of radiation therapy should ideally be at least 2 months after completion of the prior course of radiation therapy, but is left at the discretion of the treating physician depending on the patient's palliative needs. Day 1 of radiation should be on Day 1 of the next cycle of immune therapy.
- Patients with progressive disease at any time per irRC criteria will undergo a final course of radiation therapy. This may be given concurrently with a final cycle of immune therapy or as stand-alone treatment within 6 weeks after discontinuation of immune therapy but before an alternative systemic therapy is initiated.

Please see Section 5.5 below regarding situations in which these subsequent courses of radiation therapy may be withheld. Each subsequent course of radiation therapy should be given in a similar style as detailed for the initial course of radiation therapy above. In patients with a mixed response to therapy, preference will be given to an enlarging tumor (rather than one that is stable or decreasing in size) as the site of treatment. Reimaging will again be obtained after completion of the radiation therapy with timing at the discretion of the treating physicians, and the same response-adapted approach to decision making for further courses of radiation therapy will be carried out as described above.

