Measureable lesions on follow-up imaging: Per irRC specifications, new measureable lesions on follow-up imaging will be defined as being $\geq 5 \times 5$ mm in size

Index lesions: All measurable lesions up to a maximum of 10 visceral lesions (≤ 5 per organ) and 5 cutaneous lesions, should be identified as index lesions and recorded and measured at baseline. Target lesions should be selected on the basis of their size (lesions with the longest diameter), be representative of all involved organs, and lend themselves to reproducible repeated measurements. It may be the case that, on occasion, the largest lesion does not lend itself to reproducible measurement in which circumstance the next largest lesion which can be measured reproducibly should be selected. It is preferable to exclude cystic metastases as index lesions if other non-cystic lesions are available. Prior to selecting index lesions a decision should be made on which lesion will receive an initial course of radiation therapy, as this lesion is not eligible to be considered as an index lesion to assess response to immune therapy. If any subsequent course(s) of radiation therapy are given to what was previously considered an index lesion, this lesion will no longer be considered an index lesion for subsequent systemic response assessment. The rationale for this is that including irradiated lesions in response assessment would bias the assessment of a systemic effect.

Tumor Burden: At the baseline tumor assessment, the sum of the products of the two largest perpendicular diameters (SPD) of all index lesions is calculated. At each subsequent tumor assessment, the SPD of the index lesions and of new, measurable lesions are added together to provide the total tumor burden: $\text{Tumor Burden} = \text{SPD}_{\text{index lesions}} + \text{SPD}_{\text{new, measurable lesions}}$.

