11.2. Response Criteria

The irRC criteria for assessing systemic disease response (including only non-irradiated lesions) can be seen in the following table:

New, measurable lesions (ie, $\geq 5 \times 5$ mm)	Incorporated into tumor burden
New, non-measurable lesions (ie, $< 5 \times 5$ mm)	Do not define progression (but preclude irCR)
Non-index lesions	Contribute to defining irCR (complete disappearance required)
irCR	Disappearance of all lesions in two consecutive observations at least 4 weeks apart
irPR	$\geq 50\%$ decrease in tumor burden compared with baseline in two observations at least 4 weeks apart
irSD	Neither sufficient decrease in tumor burden to qualify as irPR

	nor sufficient increase in tumor burden to qualify as irPD.
irPD	$\geq 25\%$ increase in tumor burden compared with nadir (at any single time point) in two consecutive observations at least 4 weeks apart.

Examples of irRC overall response³⁷:

Measurable response Index and new, measurable lesions (tumor burden),* %	Nonmeasurable response		Overall response Using irRC
	Non-index lesions	New, nonmeasurable lesions	
↓100	Absent	Absent	irCR [†]
↓100	Stable	Any	irPR [†]
↓100	Unequivocal progression	Any	irPR [†]
↓≥50	Absent/Stable	Any	irPR [†]
↓≥50	Unequivocal progression	Any	irPR [†]
↓<50 to <25↓	Absent/Stable	Any	irSD
↓<50 to <25↓	Unequivocal progression	Any	irSD
≥25↓	Any	Any	irPD [†]

*Decreases assessed relative to baseline, including measurable lesions only (>5 x 5 mm).
†Assuming response (irCR) and progression (irPD) are confirmed by a second, consecutive assessment at least 4 wk apart.

RECIST version 1.1 will be used to assess the local response of irradiated lesions only, taking as reference the baseline largest diameter:

Complete Response (CR)	Disappearance of the irradiated lesion
Partial Response (PR)	$\geq 30\%$ decrease in the single largest diameter of the irradiated lesion
Stable Disease (SD)	Neither sufficient decrease in diameter to qualify as PR nor sufficient increase in diameter to qualify as PD
Progressive Disease (PD)	$\geq 20\%$ increase in the single largest diameter of the irradiated lesion. In addition to the relative increase of 20%, the sum must also demonstrate an absolute increase of at least 5 mm (0.5 cm).

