11.2.1. Best Overall Response

The best response recorded from the start of the treatment until disease progression/recurrence (taking as reference for progressive disease the smallest measurements recorded since the treatment started). The patient's best response assignment will depend on the achievement of both measurement and confirmation criteria.

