13. STATISTICAL CONSIDERATIONS

13.1. Study Design/Endpoints

The primary endpoint is the best overall response rate (complete and partial) after the initial course of radiation therapy with concurrent immune therapy. The secondary objectives include determination of the progression-free and overall survival at 1 year, toxicity, and quality of life. Correlative objectives include an assessment of levels of circulating CD4+, CD8+ and Treg T-cell subsets, iNOS+ macrophages, and the chemokines CCL2, CXCL9, CXCL10, and CXCL11 in relation to clinical response.

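### Removing a lesion chosen because it is growing can by itself turn stable disease into a partial response, even with a matched baseline

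*Combined protocol and SAP*

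**What the plan says.** Four rules of the combined protocol and SAP act together.

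- Section 5.3: "Patients with stable disease per irRC criteria will undergo an additional course of radiation therapy", given to a lesion not irradiated before. On the choice of lesion: "In patients with a mixed response to therapy, preference will be given to an enlarging tumor", over one that is stable or shrinking.
- Section 11.1.2 (index lesions): once an index lesion is irradiated in a later course, "this lesion will no longer be considered an index lesion for subsequent systemic response assessment". The reason given is that "including irradiated lesions in response assessment would bias the assessment of a systemic effect". No rule says how baseline or nadir is recomputed after a removal.
- Section 11.2: irPR is a fall of at least 50%, as a "decrease in tumor burden compared with baseline in two observations at least 4 weeks apart". irPD is a rise of at least 25%, as an "increase in tumor burden compared with nadir (at any single time point) in two consecutive observations at least 4 weeks apart".
- Section 11.2.1: best overall response is "The best response recorded from the start of the treatment until disease progression/recurrence", with no stop at a second course.

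The response window is worded in several ways. Section 13.1 has "best overall response rate (complete and partial) after the initial course of radiation therapy with concurrent immune therapy". Section 1.1 counts from the start of radiation therapy and the synopsis from the start of therapy. None of these says whether a response first reached on a reduced set of lesions counts.

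**The concern.** The lesion that leaves the index set is not a random one: it is preferred because it is growing. What remains is then selected for shrinkage. Using the same lesions at baseline and follow-up does not cure this, because the selection depends on what the removed lesion did before it was irradiated.

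The trial has one arm and is decided by a single count: 10 or fewer responses in 33 means ineffective (section 13.2). The 20% reference rate comes with no allowance for responses created by removing a lesion. Any such responses raise the chance of declaring activity when the full-set response rate is only 20%.

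**Working it through.** **1. The plan's own design.** Inputs from section 13.2: response rates 20% and 40%, 18 then 15 patients, ineffective at 10 or fewer of 33, probability of early termination 0.72. With stage 1 stopping at 4 or fewer responses:

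P(declare active | p) = Σ over x = 5 to 18 of Bin(x; 18, p) × P(Bin(15, p) ≥ 11 − x)

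This gives 0.0458 at p = 0.20 and 0.8011 at p = 0.40, with early termination 0.7164 at p = 0.20. The stated design reproduces. Section 13.2 words the stage 1 rule through progressions; stopping at 4 or fewer responses is the reading that yields 0.72, and it is used below.

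**2. The mechanism, with a matched baseline.** Let w be the growing lesion's share of baseline burden, g its growth, and s the shrinkage of the other index lesions together.

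- Full set: T = w(1 + g) + (1 − w)(1 − s). With the baseline sum as nadir, the patient is irSD if 0.5 < T < 1.25.
- Reduced set: (1 − s). The patient is irPR if s ≥ 0.5, once confirmed.

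Example 1 (assumed sizes): A 400 to 600, B 400 to 200, so w = 0.5, g = 0.5, s = 0.5. T = 0.75 + 0.25 = 1.00, irSD. Drop A: 200/400 = 0.50, irPR. An unchanged scan at least 4 weeks later confirms it.

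Example 2 (assumed sizes): A 400 to 500, B 600 to 270. T = 770/1000 = 0.77, irSD. Drop A: 270/600 = 0.45, a 55% fall, irPR.

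For g = 0.25, the full set is irSD when w > (s − 0.5)/(g + s):

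| Shrinkage of the rest, s | Growing lesion's share must exceed |
|---|---|
| 0.50 | 0 |
| 0.55 | 0.05/0.80 = 6% |
| 0.60 | 0.10/0.85 = 12% |
| 0.70 | 0.20/0.95 = 21% |
| 0.80 | 0.30/1.05 = 29% |

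If the rest have shrunk by less than 50%, for example 40%, the patient stays irSD after the removal.

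**3. Possible size.** The plan gives neither the frequency of mixed responses nor the spread between lesions, so every input here is assumed. Baseline products are lognormal (log SD 0.6). Each lesion's ratio to baseline is exp(μ + patient effect + lesion effect), with patient-effect SD 0.6 and μ set so that the full-set response rate is 20%. There are 200,000 patients per setting. In irSD patients with a growing lesion, the most enlarging one is removed, nothing changes afterwards, and a patient is counted if the rest are down at least 50%. Points added to the response rate:

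| Lesion-effect SD | 2–4 index lesions, any growth | 1–4 lesions, any growth | 1–4 lesions, growth ≥ 25% |
|---|---|---|---|
| 0.3 | 0.8 | 0.6 | 0.1 |
| 0.5 | 4.9 | 3.5 | 1.8 |
| 0.7 | 9.2 | 6.6 | 4.3 |

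If the growing index lesion were treated in only half of these cases, the last column would halve, to about 0.05–2 points.

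**4. Effect on the decision rule**, from the formula in step 1:

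| Apparent response rate | P(declare active) |
|---|---|
| 20% | 0.046 |
| 20.1% | 0.047 |
| 20.5% | 0.054 |
| 21% | 0.062 |
| 24% | 0.134 |
| 25% | 0.166 |
| 28% | 0.282 |
| 29% | 0.326 |

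**The case against.** **The route is narrow.** It needs at least two index lesions besides the one irradiated first, irSD on the full set, a growing index lesion that is actually treated, and the rest down by half in two observations before progression. Eligibility (4.1.2) guarantees only two measurable sites, so some patients will have a single index lesion. Treating the enlarging tumour is a preference; site preferences (5.1.2) and cumulative organ limits (5.1.4) also bear on the choice, and the tumour treated may not be an index lesion. Patients with irPD are unaffected, because best response stops at progression. All of this stands. A reader might infer that stable patients as a rule become responders; the documents support only that some can.

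**The exclusion is reasoned.** Keeping irradiated lesions would mix a local effect into a systemic measure. That justifies ignoring a lesion's size after radiation. It does not justify erasing growth that occurred before radiation, when the lesion was still a valid systemic observation.

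**The shrinking lesion may show a real systemic effect.** In example 1, unirradiated lesion B halved on combined therapy, so it would be wrong to say that such responses arise without any treatment effect. But the criterion concerns total burden, and on the full set this patient was stable.

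**Section 13.1 need not conflict with 11.2.1.** A reader might infer a contradiction between response after the initial course and response up to progression. The wording in 13.1 may only mark a starting point, as in section 1.1, so a contradiction is not established. What remains is a window worded in several ways.

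**Late responses belong to the question.** The trial tests response-adapted radiation, and 11.1.2 notes that responses can take months to appear. Excluding every response reached after a removal would be costly: if 5 or 10 of the assumed 40 points were such responses, power would fall from 0.80 to 0.61 (at 35%) or 0.37 (at 30%). That is a good argument against a broad exclusion. It does not protect a response produced by the removal itself.

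**Conclusion.** The concern holds in limited form. The rules as written let an irSD patient with two or more index lesions be scored irPR solely because the growing lesion was removed, and 11.2.1 counts this in the primary endpoint. The direction is upward only.

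The size cannot be fixed from the documents. Under the assumptions above it is about 0.1 to 9 points of response rate, so the type I error of the 11-in-33 rule lies between about 0.05, close to nominal, and about 0.33. The upper end requires wide lesion-to-lesion variation, several index lesions in every patient, any growth counted as enlarging, and the worst lesion always treated. The range should not be read as an estimate for this trial. The point warrants a precise scoring rule; it does not warrant replacing the primary endpoint.

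**What to change.** In 11.1.2 and 11.2.1, add:

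1. After an index lesion is removed, compute baseline and current burden on the same remaining lesions.
2. Do not count as a primary response any irPR or irCR whose threshold the remaining lesions already met at the last scan before the removal, when the full set was irSD.
3. Responses that the remaining lesions first reach through further shrinkage after the removal still count.

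In 13.3, report the response rate with its 95% confidence interval both with and without all responses first reached on a reduced lesion set. Use one wording of the response window in the synopsis, 1.1, 11.2.1 and 13.1, stating whether responses after a second course count.

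The cost is some endpoint text, one extra table and possibly a slightly lower response rate. The choice of lesion in 5.3 is untouched, and genuine late responses stay in the primary count. Section 11.2.3 places the response review at study completion, so the rule can be settled before that review.
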